 If subjects will be compensated for their participation, explain the method/terms of payment (e.g money; check; extra credit; gift certificate). Describe the schedule and amounts of compensation (e.g., at end of study; after each session/visit) including the total amount subjects can receive for completing the study. Specify whether subjects will be reimbursed for out-of pocket expenses. If so, describe any requirements for reimbursement (e.g., receipt). 	••,
[] Not applicable - This study involves no interaction/intervention with research subjects (i.e., involves the use of records, charts, biospecimens).	3
[] No compensation will be provided to subjects.	
[] No reimbursement will be provided to subjects.	
The study will provide subjects a compensation of \$40/visit for participation in the study. The paymenth the study will compensate subjects for their time and will be paid at the end of the fifth and final visit Irvine will pay compensation directly to patients.	
They will be paid through an electronic payment system called pay-quest. Personal information a subjects, including name, address, and social security number, will be released to the Accounting Offi UCI for the purpose of payment. Total compensation possible is \$200.	
SECTION 12: CONFIDENTIALITY OF RESEARCH DATA	
Indicate all identifiers that may be included in the research records for the study. Check all that ap	ply:
[] No subject identifiers are obtained (i.e., researchers will not collect information that can link the subjects to their data)	

[] Social Security Numbers [] Device identifiers/Serial numbers

[X] Names

[] Dates* [x] Medical record numbers [] Web URLs [X] Postal address [] Health plan numbers [] IP address numbers [X] Phone numbers [] Account numbers [] Biometric identifiers [] Fax numbers [] License/Certificate numbers [] Facial Photos/Images [] Email address [] Vehicle id numbers [] Any other unique identifier			
[] Other (Specify all):			
* birth date, treatment/hospitalization dates			
Explain how data will be recorded.			
Check all that apply:			
 [X] Paper documents/records [X] Electronic records/database [] Audio recording [] Video recording [X] Photographs [X] Biological specimens [] Other(s) (specify): 			
Indicate how data will be stored, secured including paper records, electronic files, audio/video tapes, biospecimens, etc.			
 Electronic Data (check all that apply): [X] Coded data; code key is kept separate from data in secure location. [] Data includes subject identifiable information. Note: Encryption software is required. (Provide rationale for maintaining subject identifiable info): <type here=""></type> [] Data will be stored on secure network server. [X] Data will be stored on stand alone desktop computer (not connected to network/internet) [] Other (specify here): 			
 Hardcopy Data, Recordings and Biospecimens (check all that apply): [X] Coded data; code key is kept separate from data in secure location. [] Data includes subject identifiable information (Provide rationale for maintaining subject identifiable info): <type here=""></type> [X] Data will be stored in locked file cabinet or locked room at UCI/UCIMC. [] Data will be stored locked lab/refrigerator/freezer at UCI/UCIMC. [X] Other (specify here): Tissue specimens will be de-identified before shipment to Massachusetts General Hospital for analysis. 			
 Data on Portable Devices: 4. Describe the portable device(s) to be used (e.g. laptop, PDA, iPod, portable hard drive including flash drives). 5. Specify whether subject identifiable data will be stored on the device. If so, justify why it is necessary to store subject identifiers on the device. 			
Not applicable – No study data will be maintained on portable devices.			

Data without subject identifiable information may be stored temporarily on a password protected Laptop computer. This will include results of laser therapy and pictures of study sites. Study sites are non-facial so it is unlikely subjects can be identified from photos. A laptop is necessary because the imaging of the data collection takes place in the treatment room and it is difficult to transport a desktop into the treatment. Data from the laptop will be transferred to a non-network computer for long-term storage. No subject identifiable data will be kept on the laptop.

Data Access:

- 6. Specify who, besides the entities listed below, will have access to subject identifiable private data and records.
- 7. If there is a **code key**, specify who on the research team will hold the key, and who will have access to the key.
- 8. If publications and/or presentations will include **subject identifiable information**, specify where the data will be **published and/or presented** and address how the study team will obtain permission from subjects.

[Not applicable –	No subject identifiers will be collected.	
---	------------------	---	--

[X] Not applicable – Only the entities listed above will have access to subject identifiable private data and records.

Data Retention:

9.	Explain how long subject identifiable research data will be retained.	The data may include a code
	with a separate code key or the data may include subject identifiers.	

L	Not applicable. No subject identifiable research data will be retained.
[] Destroy once data collection is completed
[] Destroy at the earliest opportunity, consistent with the conduct of this research. Specify timeframe:
[] Destroy after publication/presentation
[X] Maintain for approximately 7 years
[] Maintain in a repository indefinitely. Other researchers may have access to the data for future research. Any data shared with other researchers, will not include name or other personal identifying information. Note: Appendix M is required .
[] Research records will be retained for seven years after all children enrolled in the study reach the age of majority [age 18 in California] as this study includes children .
[] Research records will be retained 25 years after study closure as this study involves in vitro fertilization studies or research involving pregnant women.
[] As this is a FDA regulated study, research records will be retained for two years after an approved marketing application. If approval is not received, the research records will be kept for 2 years after the investigation is discontinued and the FDA is notified.
г	1 Other:

Data Destruction:

- 10. If audio or video recordings will be taken, specify the **timeframe for the transcription and/or** destruction of the audio and video recordings.
- 11. If photographs will be collected, specify the **timeframe destruction of photographs**.

 Not applicable – No audio/video recordings or photographs will be collected. Audio or video recordings transcribed; specify time frame: <type here=""></type> Audio or video recordings destroyed; specify time frame: <type here=""></type> Audio or video recordings maintained indefinitely Photographs destroyed; specify time frame: <type here=""></type> Photographs maintained indefinitely: The de-identify photographs will not be used to share with other researchers. They will be kept for reference throughout the duration of the project.

Certificate of Confidentiality:

- 12. Specify whether a Certificate of Confidentiality (COC) has been or will be requested from the NIH. If yes, explain in what situations personally identifiable information protected by a COC will be disclosed by the UCI study team.
- [X] Not applicable No COC has been requested for this study.

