There will be a total of 5 visits, about 10-11 hours over a maximum period of 18-19 weeks in length of the study. Those visits include a screening visit, a visit assessing laser tolerance, a follow-up visit within 20-48 hours of tolerability testing to ensure patient safety, a treatment visit

with resultant biopsy, and a follow-up visit after biopsy to ensure patient safety.

References:

Expected Results and Data Analysis:

We expect to demonstrate that this NIR laser dose elicits statistically significant dendritic cell trafficking to the human skin and induces cytokine/chemokine release and expression changes similar to that previously seen in mice.

The statistical end point of the study will be the changes in density of CD11c+ dermal dendritic cells between two biopsies from a study subject where one sample is subjected to laser irradiation and the other is the control. For assessment of statistical significance, we will apply a paired sample t-test.

SECTION 2: ROLES AND EXPERTISE OF THE STUDY TEAM

List all study team members below.

- 1. Identify each **member's position** (e.g., Associate Professor, graduate or undergraduate student) and **department**, and describe his or her **qualifications**, **level of training and expertise**. Include information about relevant licenses/medical privileges, as applicable.
- 2. Describe each team member's **specific role and responsibility** on the study.
- 3. **Faculty Sponsors** list as Co-Researchers and describe their role on the project; include oversight responsibilities for the research study.
- 4. Explain who will have access to subject identifiable data.
- 5. Indicate who will be involved in recruitment, informed consent process, research procedures/interventions, and analysis of data.

Lead Researcher:

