- 5. Describe how the **subject's privacy will be protected** during the research procedures. **Note**: This is not the same as confidentiality (see the Privacy and Confidentiality web page).
- 6. Be sure to submit **data collection instruments** for review with your e-IRB Application (e.g., measures, questionnaires, interview questions, observational tool, etc.).

Description of Methodology/Study Procedures

Study Design

This study will be conducted at the Beckman Laser Institute outpatient medical clinics. Subjects will be treated as per protocol with a fixed light dose. Biopsies will be performed at the same facilities. Histological analysis will be conducted by the Department of Dermatopathology at UC Irvine. Immunopathology and PCR studies of the biopsied tissue will be conducted by faculty both affiliated with this study and the Massachusettes General Hospital.

Subjects will be recruited through Beckman Laser Institute outpatient medical clinics. Those interested in learning more will be contacted by the clinical research personnel, who will provide each interested person more information on the study and discuss with the person the inclusion and exclusion criteria. If the subject is interested, they will make an appointment to come to Beckman Laser Institute outpatient medical clinics.

At the initial visit, the clinical research personnel will go through the study consent form in detail and complete the necessary informed consent documentation. If the subject is willing, he or she will undergo a brief medical screening visit including a review of medical history, current medications, and review of vital signs (blood pressure, pulse, temperature). During that screening examination, the study personnel will ensure that the subject meets all the inclusion and none of the exclusion criteria. The study personnel will determine the subject's skin phototype. As a result of this initial visit, the subject will be formally enrolled in the study and a clinical research record will be started on the subject. The initial visit will take approximately 30 minutes.

Description of the Intervention

1. Laser Treatment

Within 4 weeks of the initial screening visit, subjects will return for laser treatments.

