Prior to all laser treatments, female patients of childbearing age will be administered a urine Beta hCG urine test. A positive result will disqualify the patient from the study. These results will be intended for research purposes only and will not be included in the patients' medical record.

A 95% water polymer gel will be applied prior to all laser treatments to all laser-exposed skin in order to limit excessive heat buildup within the skin. The gel will also be applied to the control site non-treated skin that will be biopsied. Subjects and research personnel will wear protective goggles appropriate to the safety rating of the laser.

In order to determine the maximum tolerable laser irradiance to be used in the biopsy phase of the study, each subject will receive a series of 1 minute exposures on 5 mm² areas of the skin of the lower back from continuous wave 1064 nm laser light emitted by a modified handheld diode laser device (IPG Photonics). Prior to these treatments, subjects will be informed about the kind of skin sensations the laser may cause and will always be asked to indicate to the study doctor when the exposure becomes uncomfortable. In the case that an exposure produces discomfort in the subject (a tingling or pinprick sensation or uncomfortable feeling of hotness), the exposure will be terminated. After the completion of each test site, the study personnel will examine the skin surface for signs of damage or alteration. Digital photographs will be taken of all sites before and after laser treatment.

Up to five initial one-minute treatments will be given to each subject starting at 1 W/cm² and increasing at 1 W/cm² increments up to a maximum of 5 W/cm² (0.2, 0.4, 0.6, 0.8 and 1 Watt). If a subject experiences discomfort during any of these treatments, a second set of treatments will be made between the highest tolerable irradiance and the one that was not tolerable. These will be done at 0.2 W/cm² increments (e.g., 3.2, 3.4, 3.6, and 3.8 W/cm²). The highest irradiance the subject tolerates for 1 minute will be identified as that subject's maximum tolerable irradiance. After all subjects are tested, we will select the highest irradiance that is tolerated by all ten subjects and use this in the second phase of the study.

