The determination of maximum tolerable irradiance will be conducted within 6 months of the second phase of the study. At that time, all subjects will receive a single treatment to a 5 mm spot on the lower back with the CW NIR laser for one minute at the maximum tolerable irradiance. The determination of the maximum tolerable irradiance of all 10 subjects will be determined before starting the second phase of the study.

Within 20-48 hours, patients will return to clinic for a follow-up visit where the treated site will be checked to ensure no unusual reactions from the treatment have occurred.

2. Punch Biopsy

Four hours later, two 4 mm punch biopsies will be performed on the skin of the lower back: one at the location of the laser exposure (experimental) and a second one at a bilateral non-exposed skin site on the lower back (control). Biopsies will be taken using standard biopsy protocol. The skin will be cleaned and patient will receive local anesthesia for this procedure. Following completion of the biopsies, a bandage will be placed on each biopsy site. The clinical research personnel will provide the subject instructions in oral and written form on the care of the biopsy site. The subject will be seen 10-14 days after to assess the status of the biopsy site for proper healing.

In summary, there will be a total of 5 visits, about 10-11 hours total, spanning over a maximum of 18-19 weeks in length of the study. Those visits include a screening visit, a visit assessing laser tolerance, a follow-up visit within 20-48 hours of tolerability testing to ensure patient safety, a treatment visit with resultant biopsy, and a follow-up visit or phone call including photos of biopsy sites after biopsy to ensure patient safety.

3. Tissue Analysis

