Half of each biopsy sample will be fixed, paraffin embedded and prepared as thin section slides. One set of these slides will receive Hematoxylin and Eosin staining to evaluate microscopic skin changes. This analysis will be conducted by faculty affiliated with the Massachusetts General Hospital Dept. of Dermatopathology after receiving the biopsy samples immersed in formalin from UC Irvine. A second set of specimen slides, identified only by subject number, will also be sent to collaborators at the Massachusetts General Hospital Dept. of Dermatopathology for further immunohistochemical staining and analysis. The second half of each biopsy specimen will be flash frozen at -80 C. These samples will be identified only by subject number and sent to collaborators at the Massachusetts General Hospital Vaccine and Immunotherapy Center for assessment of RNA and protein expression by qPCR, which will be used to identify up-regulation of specific cytokines and chemokines such as IL-1a, IL-1b, TNFa, CCL2, CCL6, CCL11, CCL17, CCL19, CCL20, and CCR7.

B. Statistical Considerations

- 1. **Statistical Analysis Plan:** Describe the statistical method(s) for the stated specific aims and hypotheses **described in Section 1**. *Note:* Required for scientific review.
- 2. **Explain how the overall target sample size was determined** (Provide power / sample size justification for the study).

If a statistical analysis plan is not appropriate for your study design, please describe a plan for assessing your study results.

Statistical Plan and Data Analysis:

Ten subjects will be recruited for the study on skin immune response to laser treatment. This is a single-site pilot study and all subjects will be recruited through their affiliation with the researchers. Analysis of histology samples of the skin will be for exclusion of indications of skin damage and will not be used in statistical analyses. Analysis of RNA and protein expression by qPCR will be descriptive and not used in statistical analyses.

Quantitative analysis will pertain to changes in the density of CD11c+ dermal dendritic cells in the laser-treated skin as compared with non-laser treated control skin. For assessment of statistical significance, we will apply a paired sample t-test.

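### Safety follow-up: no look at the tolerability-test laser sites is scheduled after 20-48 hours, although the existing treatment visit could supply one

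*Combined protocol and SAP*

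**What the plan says.** Below, phase 1 is the tolerability testing and phase 2 is the treatment with biopsy.

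- **Section 3A, Laser Treatment, phase 1.** The start is fixed relative to screening: "Within 4 weeks of the initial screening visit, subjects will return for laser treatments". Exposures rise from 1 to 5 W/cm², with a finer second series if a step is uncomfortable. Staff inspect the skin after each test site. On photographs: "Digital photographs will be taken of all sites before and after laser treatment".
- **Section 3A, Laser Treatment, phase 2.** The highest irradiance tolerated by all ten subjects is selected, and "all subjects will receive a single treatment to a 5 mm spot on the lower back".
- **Section 3A, Laser Treatment, check at 20-48 hours.** Here "patients will return to clinic for a follow-up visit where the treated site will be checked to ensure no unusual reactions". This sentence follows the phase 2 text, but the visit lists in Sections 1 and 3A, and Section 7B, tie the visit to tolerability testing.
- **Section 3A, Punch Biopsy.** Two 4 mm punches are taken at four hours. Afterwards: "The subject will be seen 10-14 days after to assess the status of the biopsy site for proper healing". The visit summary describes this last contact as "a follow-up visit or phone call including photos of biopsy sites after biopsy to ensure patient safety". Section 1 ends its own visit list with "and a follow-up visit after biopsy to ensure patient safety".
- **Section 3B.** "Analysis of histology samples of the skin will be for exclusion of indications of skin damage and will not be used in statistical analyses".
- **Section 7B.** Blistering, scabbing and scarring are named as possible laser harms. Several reasons are given for expecting little damage: power and dose kept under known damage thresholds, stopping at discomfort, the water gel, and doses below those of other continuous-wave 1064 nm work. A 24-hour pager is provided.

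**The concern.** The protocol names three skin harms, and at least one of them (scarring) is a late outcome. Yet the sites with the highest irradiances are looked at for two days at most. Later contacts exist, but none is directed at those sites. The treatment visit lists only the exposure and the biopsies, and the final contact is about biopsy healing and may be a phone call with photographs.

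Two things are at stake, both modest. One is safety ascertainment: a persistent mark would be recorded only if the subject or a member of staff happened to notice and report it. The other is the wording of the report. The Specific Aim describes the dose as non-damaging, and a reader should be told how long the skin was watched. That description is not an endpoint, so no hypothesis test depends on it.

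**Working it through.** **Plan's own figure.** The plan computes nothing on this point. Its only calculation is the sample size. Reading the 108% change as a difference of 1.08 with SD of differences 1.0, a paired t-test at two-sided 0.05 (noncentral t) needs n = 9 (power 80.9%), as stated. Nothing below uses that figure.

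**Step 1. Scheduled looks at exposed skin.**

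| Time | Phase 1 sites | Phase 2 spot |
|---|---|---|
| Around exposure | examined after each exposure; photographed | photographed |
| 4 hours | none scheduled | 4 mm punch; histology to exclude damage |
| 20-48 hours after phase 1 | checked | not yet treated |
| Treatment visit | not mentioned | exposed and biopsied |
| 10-14 days after biopsy | not mentioned | biopsy wound, possibly by phone and photos |

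The last scheduled look at intact exposed skin is therefore at 48 hours or earlier. The Section 7B sentence promising close monitoring refers back to the listed procedures and adds no examination.

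**Step 2. Can the phase 2 spot fill the gap?** Power divided by irradiance gives the spot area: 0.2 W / 1 W/cm² = 0.2 cm² = 20 mm². This agrees with a 5 mm diameter, π × 2.5² = 19.63 mm². A centred 4 mm punch removes π × 2² = 12.57 mm², a fraction of 16/25 = 64%. It leaves 36% as a rim (5 − 4)/2 = 0.5 mm wide around a healing wound. Section 3A also gives the phase 1 areas as 5 mm². A spot of that area is about 2.5 mm across, and the punch would remove all of it. On either reading no intact phase 2 site remains to be judged at 10-14 days.

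The histology covers one irradiance at four hours. Unless all ten subjects tolerate 5 W/cm², some phase 1 sites, including those stopped for discomfort, will have had a higher irradiance than the histology covers. Exposures stopped early were also shorter than one minute.

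**Step 3. How many phase 1 sites?** Assume a separate site per exposure and that each series stops at first discomfort. With no discomfort there are 5 sites. With first discomfort at step k (1 to 5) there are k sites plus 1 to 4 finer steps: 2 to 5 for k = 1, and 6 to 9 for k = 5. The overall range is 2 to 9 per subject.

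**Step 4. How old would the sites be at the treatment visit?** Maximum age in weeks = total study length − screening gap − biopsy follow-up.

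- 18 − 4 − 2 = 12.0
- 19 − 4 − 10/7 = 13.6
- 18 − 0 − 2 = 16.0
- 19 − 0 − 10/7 = 17.6

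The separate six-month limit between phases would allow about 26 weeks. These are maxima. No minimum is stated, so for the last subjects tested the gap could be days.

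**Step 5. Expected frequency.** Section 7B says that at 43° C damage would take over an hour. Against a one-minute exposure the margin is over 60/1, more than 60-fold. The same section says only that temperatures will not generally exceed that level, so the margin is an expectation and not a guarantee.

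**The case against.** The strongest case against is that this is a preference about safety follow-up in a study that already has layered protection. Exposure stops at discomfort, a gel limits heating, every site is inspected, photographs are taken, a 20-48 hour visit follows, histology checks the selected dose, and a pager and adverse-event handling cover the rest. The doses are described as well under those of other continuous-wave studies and under damage thresholds. Section 1 cites a published finding that roughly equivalent exposure was tolerated without damage in humans. Staff will also see the same lower back at the treatment visit. All of this stands, and it is why the priority is low. It does not put a late look into the schedule.

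Four stronger readings are tempting but unsupported:

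- **That 48 hours is too early for every listed harm.** The documents give no onset times. Early crusting might be visible by 48 hours, and nothing shows that blistering would be missed.
- **That the cited human pilot is uninformative because it enrolled phototypes V-VI.** Section 4B chooses phototypes I/II for minimal melanin, so V-VI skin is not an obviously easier test. The pilot does differ in pulse mode (nanosecond pulses) and irradiance (up to 3.84 W/cm²).
- **That the cited studies had no late follow-up.** Section 7B reports only that they described no immediate thermal damage. What else they observed cannot be seen here.
- **That phase 1 findings decide whether the phase 2 dose is non-damaging.** Sites above the selected irradiance do not bear on that dose.

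**Conclusion.** The gap is real and small. No assessment of the phase 1 laser sites is scheduled after 20-48 hours, and neither the phase 2 histology nor the final contact replaces one. This is a matter of safety follow-up, not of analysis: the paired t-test and N = 10 are unaffected.

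Confidence is high on the schedule, which rests on the text alone. It is lower on the consequence, because the view that 48 hours is too early is clinical judgement, firm for scarring and weaker for scabbing. A reader might infer that the dose is unsafe or that late damage is likely. The documents support neither, and late damage is expected to be rare. The change is worth making because it costs little.

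**What to change.** 1. **Section 3A.** At the existing treatment visit, before the phase 2 exposure, examine and photograph each subject's phase 1 sites, using the phase 1 photographs to locate them. Record any persistent change with its irradiance and the days since exposure, or record that the site could not be found. If fewer than 14 days have passed, include these sites in the 10-14 day contact and its photographs.
2. **Section 3B.** List the immediate, 20-48 hour and late findings descriptively by subject, separating sites at or below the selected irradiance from those above it. No interval estimate is needed.
3. **Reporting.** State the observation time wherever the dose is called non-damaging.

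**Cost.** Two or three sentences, and an assumed few minutes per subject, with no new visit or biopsy. The timing of the late look will vary because no minimum gap between phases is stated. Some unmarked sites may not be found again. Subjects who leave before phase 2 will be missed. The safety statement becomes less categorical.
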